2.2.2. Secondary Objective

To evaluate safety and tolerability following short-term exposure to darolutamide (ODM-201) in female patients with EBC.

2.3. Sample Size

Up to 60 patients (a minimum of eight evaluable patients, and up to 20 patients in each BC Subtype: triple-negative, HR+/HER2 negative, HER2 positive) will be required for the performance of the molecular trials and possible hypothesis generation.

At the time of enrollment closure on 14 February 2019, 36 patients were enrolled with the following characteristics per local or central assessment: seven triple-negative, 19 HR+/HER2 negative, and 10 HER2 positive. Although the triple-negative subgroup did not reach the minimum number of eight planned patients as per protocol, it was deemed acceptable for the following reasons:

- The primary objective of the study is to identify the molecular alterations that occur in human BC tissue, following short-term exposure to darolutamide in female patients with EBC. There are no efficacy objectives in this trial.
- The number of patients per cohort was not defined after a formal sample size calculation, but was a number considered appropriate for the performance of the molecular studies according to the recommendations by the central laboratory responsible for the molecular analyses.
- The central laboratory now considers that seven patients in the triple-negative cohort is sufficient to perform the evaluation of the molecular alterations, and to eventually

generate the relevant hypothesis in this subgroup. Seven patients is then deemed sufficient to adequately characterize the study objectives in this tissue-acquisition window of opportunity study.

- The Sponsor, along with the Study Chair, have determined that trial objectives have been reached in terms of the sample banking needed for biomarker analyses.
- In terms of statistical analysis (specifically the safety profile), there is no comparison between subgroups, so this change will have no effect to the final analysis.

2.4. Timing of Analyses

Safety outputs will be generated for data review performed by the Study Steering Committee (SSC) once 20, around 35, and once all patients have been enrolled and undergone the End of Study (EoS) as per protocol.

A Final Safety Analysis will be performed when all patients have completed the trial.

3. Statistical Methods

3.1. Analysis Population

3.1.1. Intention-to-Treat Population

The **Intention-to-Treat (ITT) Population** includes all patients who are enrolled in the trial, regardless of whether they actually received investigational medication. This population will be identified using the Intent-to-Treat Population Flag (ITTF) as defined in Subject-Level Analysis Dataset (ADSL) according to Analysis Data Model (ADaM).

3.1.2. Safety Population

The **Safety Population** includes all patients who receive at least one tablet of darolutamide, and will be used for the analysis of safety data of the trial. This population set will be identified using the Safety Population Flag (SAFF) as defined in ADSL according to ADaM.

3.1.3. Evaluable Population

The **Evaluable Population** includes all patients who satisfied the following criteria:

- Minimum duration of treatment with darolutamide is 14 days, with a minimum of 10 consecutive days of treatment prior to the definitive surgery.
- Mandatory tumor tissue is collected at screening and at surgery according to the protocol and submitted to the central laboratory.
- Adequacy for molecular assessment of the tumor tissue collected before and after the protocol treatment initiation. The adequacy will be evaluated by the central laboratory.

The evaluable population will be used for the performance of molecular trials and possible hypothesis generation. More information regarding Molecular Analyses will be discussed in a separate document.

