	Up to 60 patients (a minimum of 8 evaluable patients and up to 20 patients in each breast cancer subtype: triple-negative, HR+/HER2 negative, HER2 positive) will be required for the performance of the molecular studies and possible hypothesis generation. A patient will be considered evaluable if the following criteria are met: 
▪ Minimum duration of treatment with darolutamide is of 14 days, with a minimum of 10 consecutive days of treatment prior to the definitive BC surgery/pre-NAST biopsy.▪ Mandatory tumor tissue is collected at screening and at BC surgery/pre-NAST biopsy according to the protocol and submitted to the central lab.▪ Adequacy for molecular assessment of the tumor tissue collected before and after the protocol treatment initiation. The adequacy will be evaluated by the central lab. Assessment of patient evalability, safety and distribution of patients with respect to hormone receptor status and HER2 status will be performed by the Study Steering Committee (SSC) at given time points depending on the recruitment, primarily planned once 20, around 35 and once all patients have been enrolled and undergone the EoS per protocol. This will allow for the SSC to ascertain that the appropriate number of evaluable patients is being accrued, that more or less patients may be required, or in the extreme case, that accrual should close if the patient evalability rate is very low and/or safety concerns arise. The SSC will define the evalability of patients that discontinue treatment more than 3 days before surgery: molecular analyses may be taken into consideration for the decision about the evalability of such patients.						
Study Populations	Study Populations 
▪ Intention-to-treat (ITT) Population: the ITT population includes all patients who are enrolled in the study regardless of whether they have been treated or not.▪ Safety Population: the Safety population includes all patients who have taken at least one						

	tablet of darolutamide.
--	-------------------------

- Evaluable population: includes all patients who are considered evaluable per protocol.

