6.4.4 BC Surgery/Pre-NAST biopsy

Surgery will be done according to site standards. In patients not receiving NAST, BC tissue will be collected at time of surgery according to section 6.5.7. In patients receiving NAST, a breast tumor sample will be collected during the pre-NAST biopsy (refer to section 6.5.7) after completing darolutamide and before NAST start. As much as possible, sites should avoid scheduling BC surgery/pre-NAST biopsy on Mondays or on the day following a holiday, so that Pre-surgery visit may take place the day prior to BC surgery/pre-NAST biopsy according to section 6.4.3.

In the event that a sentinel lymph node biopsy (SLNB) is performed, periareolar injection is to be conducted. The dye/colloid should not be injected into the tumor itself as this may alter the tissue and affect the molecular analyses to be performed on tumor tissue sample.

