6.5.7.1 Breast Tumor Tissue Collection

Collection of the following samples is mandatory in the study:

- **Pre-treatment:** A breast tumor sample must be collected at the time of the initial diagnosis (or in a subsequent procedure) either by core needle or incisional biopsy. Excisional biopsy will not be allowed.

A minimum of 3 core biopsies using a 14-gauge needle (or the equivalent with an incisional biopsy) is recommended to perform the protocol-defined molecular analyses. Once the core biopsies have been removed, two of the cores (or equivalent amount of tumor) must be immediately snap-frozen using the procedure outlined in the study laboratory manual, then stored in liquid nitrogen or at -70 to -80 degrees Celsius at the site. The third sample should be prepared in paraffin according to site's practice. In cases it is not possible to provide enough material, collection of 2 cores (or equivalent amount with incisional biopsy) will be acceptable: one core will be snap-frozen and the other one will be prepared in paraffin.

In patients with multifocal or multicentric tumors, efforts will be made to obtain samples from each discrete lesion.

For patients who already had the confirmatory biopsy prior to registration, there is no need to repeat it provided that their diagnostic biopsy has been done according to the protocol requirements (in terms of number of cores/tissue, fresh frozen collection, etc.).

- **BC surgery/Pre-NAST biopsy:** An amount of BC tissue equivalent to two cores (or 2 cores of tissue) must be collected at the time of the patient's surgery (if no NAST indicated) or at time of the pre-NAST biopsy (if NAST is indicated). The pre-NAST biopsy should be done before NAST start. Half of the tissue will be prepared as fresh-frozen, the other half in paraffin.

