8. STATISTICAL CONSIDERATIONS

8.1 Study Populations

- Intention-to-treat (ITT) Population: The ITT population includes all patients who are enrolled in the study regardless of whether they have been treated or not.
- Safety Population: The Safety population includes all patients who have taken at least one tablet of darolutamide.
- Evaluable population: Includes all patients who satisfied all criteria in section 8.5.

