8.5 Sample Size

The primary objective of this trial is to evaluate molecular alterations occurring in BC tissue following short-term darolutamide administration.

Up to 60 patients (minimum of 8 but up to 20 patients in each BC subtype: triple-negative, HR+/HER2 negative, HER2 positive) will be required for the performance of the molecular studies and possible hypothesis generation.

A patient will be considered evaluable if the following criteria are met:

- Minimum duration of treatment with darolutamide is of 14 days, with a minimum of 10 consecutive days of treatment prior to the definitive BC surgery/pre-NAST biopsy.
- Mandatory tumor tissue is collected at screening and at BC surgery/pre-NAST biopsy according to the protocol and submitted to the central laboratory.
- Adequacy for molecular assessment of the tumor tissue collected before and after the protocol treatment initiation. The adequacy will be evaluated by the central laboratory.

Assessment of patient evaliability, safety and distribution of patients with respect to hormone receptor status and HER2 status will be performed by the SSC at given time points depending on the recruitment, for example once 20, around 35 and once all patients have been enrolled and undergone the EoS per protocol. This will allow SSC to ascertain that the appropriate number of evaluable patients is being accrued, that more or less patients may be required, or in the extreme case, that accrual should close if the patient evaliability rate is very low and/or safety concerns arise.

The SSC will define the evaliability of patients that discontinue treatment more than 3 days before BC surgery/pre-NAST biopsy; molecular analyses may be taken into consideration for the decision about the evaliability of such patients.

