| Eligibility Criteria | 
Inclusion Criteria
 
 1. Signed and dated PICF obtained prior to initiation of any study-specific procedure and treatment. 2. Female \geq 18 years old. 3. Histologically proven invasive breast carcinoma (through either a core needle biopsy or an incisional biopsy) for which surgery is indicated as the primary treatment modality. Patients for which NAST is indicated are also eligible provided they are willing to undergo a biopsy after completing treatment with darolutamide and prior to NAST start. 4. Known ER, PgR and HER2 statuses. 5. Tumor must be confined to either the breast or to the breast and ipsilateral axilla (Note: patients with multifocal/multicentric tumors are eligible). Patient must have (according to TNM 7th edition rules): 
 ▪ T1 with $T \geq 1.0$ cm, T2 or T3 by at least one radiographic or clinical measurement ▪ Either clinically positive (N1 only) or clinically negative axillary nodes (N0) ▪ M0 6. Eastern Cooperative Oncology Group (ECOG) performance status (PS) of 0 or 1. 7. Adequate organ function within 28 days prior to enrollment, as defined by the following criteria: 
 ▪ Hematology: Hemoglobin ≥ 9.0 g/dL, Absolute neutrophil count (ANC) $\geq 1.5 \times 10^9/L$, Platelet count $\geq 100 \times 10^9/L$ ▪ Liver function: Alanine aminotransferase (ALT) and aspartate transaminase (AST) $\leq 2.5 \times$ upper limit of normal (ULN), Total bilirubin $\leq 1.5 \times$ ULN (or ≤ 3 times ULN for patients with documented Gilbert's syndrome or for whom indirect bilirubin concentrations suggest an extra-hepatic source of elevation). ▪ Renal function: Creatinine $\leq 2.0 \times$ ULN 8. No more than 42 days should elapse from the day the study-specific tumor sample is taken at initial diagnosis (or subsequent procedure) to the day of the first intake of darolutamide. 9. Women of childbearing potential (WoCBP) must agree to use acceptable non-hormonal contraceptive methods of birth control from the day of the screening pregnancy test and up to 3 months after the last intake of darolutamide. 10. For WoCBP negative serum pregnancy test within 7 days of enrollment. 11. Willingness and ability to comply with scheduled visits, treatment plans, laboratory tests, and biopsies as detailed in the protocol. 
Exclusion Criteria
 
 1. Any T0, Tis, T1 < 1.0 cm, T4; or N2-3; or M1 BC. 2. Bilateral invasive BC. 3. Patient that underwent excisional biopsy of the primary tumor. 4. Medical indication or patient desire to undergo BC surgery or start NAST prior to completing at least 14 days of treatment with darolutamide, and/or refusal of patient to undergo corresponding biopsy in case NAST is planned. |

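### SAP 3.1.3 ties evaluability to surgery alone, while the protocol's definition also accepts the pre-NAST biopsy that supplies NAST patients' post-treatment tissue

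*SAP*

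**What the plan says.** SAP 3.1.3 sets three criteria for the Evaluable Population. The first asks for at least 14 days of darolutamide, "with a minimum of 10 consecutive days of treatment prior to the definitive surgery". The second is "Mandatory tumor tissue is collected at screening and at surgery according to the protocol and submitted to the central laboratory". The third leaves tissue adequacy to the central laboratory and names no procedure.

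Protocol 8.1 defines the same population by cross-reference: "Evaluable population: Includes all patients who satisfied all criteria in section 8.5". The first two criteria in protocol 8.5 read "with a minimum of 10 consecutive days of treatment prior to the definitive BC surgery/pre-NAST biopsy" and "Mandatory tumor tissue is collected at screening and at BC surgery/pre-NAST biopsy according to the protocol and submitted to the central laboratory". The protocol synopsis and SAP Appendix 5.2 (the v5.0 Germany synopsis) also name both procedures. SAP Appendix 5.1 (the v3.0 synopsis) names surgery only, as SAP 3.1.3 does.

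On who gives tissue when, inclusion criterion 3, as reproduced in Appendix 5.1, says: "Patients for which NAST is indicated are also eligible provided they are willing to undergo a biopsy after completing treatment with darolutamide". Protocol 6.4.4 adds: "In patients receiving NAST, a breast tumor sample will be collected during the pre-NAST biopsy". Protocol 6.5.7.1 places the mandatory post-treatment collection at "surgery (if no NAST indicated) or at time of the pre-NAST biopsy (if NAST is indicated".

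**The concern.** The protocol treats surgery and the pre-NAST biopsy as alternative collection points, and the patient's planned treatment decides which one applies. A population rule that names only surgery leaves out the collection point of every patient on the NAST route. If the rule were applied as written, eligible patients who completed darolutamide and gave both mandatory samples would still be counted as non-evaluable. The SAP's Evaluable counts would then disagree with the protocol's definition. The SAP would also disagree with itself, because its two appended synopses word this rule differently.

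**Working it through.** **1. The wording side by side.** Two criteria name a procedure, and they appear in five places.

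| Place | Treatment-run criterion | Tissue criterion |
|---|---|---|
| Protocol synopsis, Statistical Methods | surgery or pre-NAST biopsy | surgery or pre-NAST biopsy |
| Protocol 8.5 | surgery or pre-NAST biopsy | surgery or pre-NAST biopsy |
| SAP Appendix 5.2 | surgery or pre-NAST biopsy | surgery or pre-NAST biopsy |
| SAP 3.1.3 | surgery only | surgery only |
| SAP Appendix 5.1 | surgery only | surgery only |

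That is 5 × 2 = 10 statements: 3 × 2 = 6 name the biopsy and 2 × 2 = 4 do not. Appendix 5.1 also conflicts with its own Study Design text, which has tissue collected before NAST starts when NAST is indicated.

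**2. The tissue criterion applied to a NAST patient.** Her post-treatment study sample is the pre-NAST biopsy (protocol 6.4.4 and 6.5.7.1). Protocol 6.5.7.1 calls for a study sample at surgery only when NAST is not indicated. Taken literally, the criterion therefore cannot be met by any NAST patient.

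**3. The treatment-run criterion applied to the same patient.** There are two readings.
- If the 10 consecutive days may fall at any time before surgery, she meets it, because her darolutamide precedes the biopsy, NAST and any later operation.
- If the days must come immediately before surgery, she fails it, because darolutamide stops by the day before the pre-NAST biopsy (protocol 5.3.2.1).

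The text does not say which reading is meant. This criterion could exclude NAST patients too, but that cannot be asserted.

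**4. Bounds on the number affected.** SAP 2.3 gives 7 triple-negative, 19 HR+/HER2 negative and 10 HER2 positive patients, and 7 + 19 + 10 = 36 reproduces its stated total. Let K be the number of NAST patients among the 36.
- Intended reading: 0 affected, and up to 36 can be evaluable, subject to the other criteria.
- Literal reading: K affected, and at most 36 − K can be evaluable.

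The documents do not give K.

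**5. Where the population is used.**
- SAP 3.3.1 and the Patient Disposition table in SAP 4.1 count it by subtype.
- The Patient Accountability listing in SAP 4.2 shows population indicators without naming them, so Evaluable may or may not be among them.
- SAP 3.5 runs all safety analyses on the Safety Population, which is defined by taking at least one tablet. No safety denominator depends on this wording.
- SAP 3.1.3 and protocol 8.6 assign the Evaluable population to the molecular analyses. The SAP covers only the secondary objective (SAP 1) and leaves the molecular detail to a separate document.

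**The case against.** The strongest reply is that the documents already make the meaning clear. The tissue criterion speaks of mandatory tissue and refers to the protocol, and protocol 6.5.7.1 lists the pre-NAST biopsy among the mandatory samples. The documents also use the word surgery as shorthand for both procedures. The protocol synopsis and Appendix 5.2 do so in their sentence on patients who stop treatment early, where protocol 8.5 names both. Protocol 3.1 does so when describing delays, and the Pre-surgery visit serves both routes. Evaluability is assessed by the steering committee and tissue adequacy by the central laboratory, so nothing shows that the SAP's wording would decide any patient's status.

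Much of this stands. It makes the intended reading the likelier one and puts the lower bound at 0. It does not correct the rule. The reference to the protocol can be read as describing how tissue is collected rather than at which procedure, and the treatment-run criterion carries no such reference. A population definition should not depend on the reader recognising shorthand.

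A reader might infer more, in three ways that the documents do not support.
- **That the primary analysis loses its NAST patients.** This depends on whether the molecular document takes its population from SAP 3.1.3 or from protocol 8.5, and that document is not supplied.
- **That a cohort drops below the minimum of eight evaluable patients.** K is unknown, overall and by cohort. The 7/19/10 counts rest on local or central assessment, while SAP 3.3 uses the central subtype. Enrollment had already closed, and SAP 2.3 had already accepted seven triple-negative patients.
- **That the SAP deliberately narrowed the population.** SAP 3.1.3 gives no reason for a different rule, and Appendix 5.2 of the same SAP keeps the full wording.

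**Conclusion.** The inconsistency is real and minor. In two criteria SAP 3.1.3 states a narrower rule than the definition it should implement. Read literally, the tissue criterion makes all NAST patients non-evaluable; the treatment-run criterion could do the same under one of its two readings. The number affected runs from 0 to the number of NAST patients among 36 enrolled.

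Within the SAP's own outputs the consequence is confined to the Evaluable counts by subtype and, if Evaluable is one of the listed indicators, the accountability listing. No safety result changes. For the primary-objective molecular analyses an effect can be neither shown nor excluded.

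This conclusion takes protocol 8.5 as governing, as protocol 8.1 provides. Confidence is high for the difference in wording and does not extend to any actual misclassification, which the documents do not show.

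**What to change.** Replace the procedure wording in both criteria of SAP 3.1.3 with that of protocol 8.5: "with a minimum of 10 consecutive days of treatment prior to the definitive BC surgery/pre-NAST biopsy" and "Mandatory tumor tissue is collected at screening and at BC surgery/pre-NAST biopsy according to the protocol and submitted to the central laboratory". Evaluability is then tied to the procedure that supplied the post-treatment tissue.

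Appendix 5.1 is presented as a reproduction of the v3.0 synopsis, so check its two matching criteria against that source before changing them, and reconcile them with the protocol. Confirm in writing that the molecular analysis document uses the protocol 8.5 definition.

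The cost is two phrases in SAP 3.1.3, up to two in Appendix 5.1, and one confirmation. No analysis is added. SAP 3.1.3 names no dataset flag for this population, and the status is settled by the steering committee and the central laboratory, so the documents do not show that any programming would change.

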3.2. Data Handling

3.2.1. Baseline Assessment/Measurement

The last available assessment/measurement of a particular data point on or prior to the latter of the date of enrollment and the date of first dose of investigational treatment. If the patient has no value as defined above, the baseline value will be missing.

3.2.2. Date of First Dose

The date of first dose (of investigational drug) is derived as the first date when a non-zero and non-missing dose of investigational drug is administered. This is also referred to as the start of the treatment.

3.2.3. Date of Last Dose

The date of last dose (of investigational drug) is derived as the last date when a non-zero and non-missing dose of investigational drug is administered.

3.2.4. Duration

Duration, except for duration of treatment, is calculated as:

- Duration (days): (End Date – Start Date + 1).
- Duration (weeks): (End Date – Start Date + 1) / 7
- Duration (months): (End Date – Start Date + 1) / 30.4375
- Duration (years): (End Date – Start Date + 1) / 365.25

3.2.5. Missing Data

All analyses and descriptive summaries will be based on the observed data. Unless otherwise specified, missing data will not be imputed or “carried forward.”

3.2.6. Partial Dates

Only partial or missing dates for Adverse Events (AE) and Concomitant Medications (CM) will be imputed according to the following:

3.2.6.1. Imputation Rules for Partial or Missing Stop Dates:

If the month and year are present, impute the last day of that month.

If only the year is present, impute December 31 of that year.

If the stop date is entirely missing, assume the event or medication is ongoing.

If a partial or complete stop date is present and the ‘ongoing’ box is checked, then it will be assumed that the AE or CM stopped and the stop date will be imputed if partial.

| | | | | | |
|----------------|---------------------------|-----------|----|-----------------|-------------|
| Originated by: | [name] | Revision: | 03 | Effective Date: | 30 Sep 2019 |
| Doc Number: | TRIO030-DM-0025 | | | | |
| Title: | Statistical Analysis Plan | | | | |

